1) Protocol Title

Effects of liposomal bupivacaine for acute pain in hip and femur fractures: a randomized, active comparator-controlled, blinded trial

DoD Additional Requirement:

This is an investigator initiated, single-center study funded by the United States Department of Defense Health Program. The UC Davis PI and research staff are aware of specific DoD requirements and confirm that all additional criteria for DoD research have been met.

2) Author of Protocol

- UC Davis Researcher**
- Researcher from other institution**
- Private Sponsor**
- Cooperative Group**
- Other: Volunteer Associate Clinical Professor**

3) IRB Review History

This is our first revision to the initial submission to the IRB.

4) Objectives

This is an investigator-initiated, single-center, randomized, patient blinded, controlled trial. The purpose of this study is to compare the effect of a fascia iliaca compartment block (FICB) using 0.2% ropivacaine vs. liposomal bupivacaine in patients with femur and/or hip fractures admitted to the University of California Davis Medical Center (UCDMC). The primary endpoint will be the total opioid requirements during the 96 hour randomization period with secondary endpoints including total daily opioid requirements for days 1-4, duration of effect and objective pain scores using the numeric rating scale (NRS) during their hospital stay.

Hypothesis: In patients with femur or hip fractures, a fascia iliaca compartment block using liposomal bupivacaine will result in less total opioid administration during the randomization period compared to a fascia iliaca compartment block using 0.2% ropivacaine.

The long-term goal of this study is to provide pilot information to guide and design larger, multicenter trials which will evaluate the utility and cost-effectiveness of long acting liposomal bupivacaine as an opioid-sparring analgesic strategy in injured trauma patients. Ultimately, it is hoped that this information can improve safe and effective narcotic sparing analgesia in the awake, combat casualty, as well as serve as primary steps towards

evaluating broader considerations for liposomal analgesia to improve short- and long-term outcomes in these patients.

5) Background

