- 14) Pediatric patients <18 years old
- 15) Patients exhibiting signs of shock upon admission, HR >120 or SBP <100 mmHg.
- 16) History of allergic reaction to local anesthetics
- 17) Administration of any other local anesthetic in the 2 hours prior to the study enrollment.
- 18) Distal femur fractures

7) Number of Subjects

17 patients per arm

Total subjects: 34

8) Recruitment Methods

Subjects will be recruited from the UC Davis Trauma Center. Patients found to have femur and /or hip fractures admitted to UCDMC will be screened for eligibility.

Waiver of HIPAA authorization for recruitment is requested for access to PHI during the screening to determine eligibility.

Description of PHI that will be accessed.

Information reviewed to assess eligibility will include: date of admission, date of birth, gender, mechanism of trauma injury (blunt/penetrating), x-rays, lab results, admission vital signs, home medications and the patient's medical history.

The use of PHI involves no more than minimal risk and granting of waiver will not adversely affect privacy of the patients.

Access to medical records that contain patient's personal information for the purpose of this study will be limited to the approved research personnel. These personnel already have knowledge of and access to identifiable medical information of current trauma patients as part of their daily job functions; hence, granting of this waiver will not adversely affect the privacy of the involved patients or the confidentiality of their information. EMR access to PHI is password-protected and no PHI will be reused or disclosed to any

other person or entity, except as required by law. Data will be used solely for the purposes of determining study eligibility.

The research could not practicably be conducted without a waiver or alteration.

Without an initial review of the medical record for screening purposes, it would not be possible to identify potential subjects and confirm their applicability for study participation.

The research could not practicably be conducted without access to and use of PHI.

Since PHI is embedded in the medical record and since the screening process requires detailed information about trauma patients, access to medical records (viewing of PHI) is necessary.

9) Compensation to the Subjects

Subjects will not be compensated for this study.

10) Study Timelines

The duration of each subject's participation is the length of their hospital stay.

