Duration anticipated to enroll all study subjects: 12 months.

Data acquisition and analysis: same 12 months

Manuscript preparation: 6 months

Total time requirement: 1.5 years

11) Study Endpoints

Hypothesis: In patients with femur or hip fractures, a fascia iliaca compartment block using liposomal bupivacaine will require less total opioid administration compared to a fascia iliaca block using 0.2% ropivacaine.

Primary Endpoint

(1) Total opioid requirement during the 96 hour randomization period measured in milligram morphine equivalents.

Secondary Endpoint

(1) Percentage of time during the 96 hour randomization period that the objective pain score was above mild (defined as a numeric rating score >4).

12) Procedures Involved

The nature of the risks and benefits associated with participation in the study will be explained to all potential study subjects. Written informed consent must be obtained before the subject can begin any screening procedures that are not considered standard patient care. Subjects who have undergone the screening procedures and have met the entry criteria will be randomized into the study and assigned to treatment by the Unblinded Pharmacist. Subjects will be randomized in a computer-generated, blinded block, 1:1 ratio to treatment with 60mL of either 0.2% ropivacaine (120mg) or a dilution of liposomal bupivacaine (266mg).

The Pharmacy and Emergency Medicine (EM) members will be the only unblinded study team members. All other members, including the Trauma team and Clinical Research Coordinator (CRC), will remain blinded.

The unblinded Investigational Drug Service (IDS) Pharmacy at UC Davis Health (UCDH) will be responsible for blinding and drug preparation. Investigational Product (IP) will be prepared in three 35mL Luer lok syringes, each containing 20mL of IP, for a total dose of 60mL. In addition to a patient-specific institutional label, masking/amber tape will also be affixed to the syringes in order to reduce the risk of drug recognition by a supporting procedure nurse. During the procedure, nursing care of the patient will temporarily transition from the primary bedside nurse to a supporting procedure nurse. The supporting procedure nurse will remain blinded and will assist primarily with assessments and recording of vital signs (but will not work directly with the IP).

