The patient will be blinded and all members of the healthcare team will be blinded from the point of transfer of care from the Emergency Department physicians to the receiving service.

Both groups will be able to receive as needed analgesia per the primary attending service. (e.g., oral hydrocodone/acetaminophen 5/325 mg or narcotic IV push as needed for breakthrough pain).

Patients enrolled in the study will be given a light blue wristband for identification to alert physicians regarding restrictions for anesthetics. Additionally, an automatic alert notification will be given by the Electronic

Medical Record system if additional local anesthetics are ordered for the patient.

Pain Assessment

Objective pain assessment will be evaluated by the UCDMC nursing staff per local standard of care which is every four hours while the patient is awake using a numeric rating scale (NRS) of 0 to 10 with a pain score of 0 being defined as: no pain, 1-4 mild pain, 5-7 defined as moderate pain, and 8-10 defined as severe pain.

Study Definitions

Acute and hospital-related adverse effects and study outcomes will be collected and tracked prospectively during the FICB and throughout the hospital stay, as appropriate per endpoint.

During hospital stay study outcomes

Data collection will include total amount of opioids administered to study patients in morphine equivalents (see Appendix) and the use of other analgesic medications during this time period. Adjunctive analgesic use including non-steroidal anti-inflammatory drugs, acetaminophen, and gabapentin will be quantified. Use of additional adjunctive agents such as muscle relaxants also will be collected.

All objective pain and agitation scores reported by the NRS will be collected; duration of supplemental oxygen requirement; number of episodes of oxygen desaturation (arterial O₂ sat below 92%); morning incentive spirometer and peak flow measurements; 24-hour antiemetic (e.g., promethazine; ondansetron) pharmacotherapy; time to first bowel movement; and need for anti-hallucination or anti-delirium pharmacotherapy.

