Additional outcomes: hospital lengths of stay; time from study drug initiation to maximum allowable ambulation per injury pattern; post-discharge opioid type and dosage provided at the time hospital discharge prescription; and patient report of chronic pain syndromes. Adverse effects including the incidence of hypertension requiring antihypertensive pharmacotherapy in addition to the patients home regimen, hypotension (SBP < 90 mmHg) requiring fluid bolus/vasoactive pharmacotherapy, tachycardia requiring pharmacologic intervention (defined as HR greater than 100 bpm), bradycardia (defined as HR below 60 beats per minute with symptoms or hypotension), respiratory depression (apnea; transition to higher level of respiratory support), emesis, hallucinatory reactions or experiences per patient interview, and pruritus per physical exam.

The study will be stopped if ≥2 patients receiving the active study drug develop the same Grade 3 adverse reaction (Adverse Event Severity

Definition defined previously) or if one patient develops a Grade 4 or higher adverse reaction.

13) Data and Specimen Banking

Not applicable.

14) Data Management and Confidentiality

Each patient will be assigned a unique study ID number at the time of study entry. Study information stored by the research personnel at UCDMC, which may include name and medical record number, will be kept strictly confidential and available only to the principal investigator and trained staff assigned to this study. All information will be kept secure in locked file cabinets accessible only by research personnel. All identifiers for recruitment purposes will be destroyed within 2 years of completion of study.

Statistical Analysis

Data will be presented as means \pm standard errors of the mean (primary endpoint) and proportions \pm interquartile ranges (secondary endpoint). Following assessment for normality, primary endpoint data will either be subjected to parametric unpaired two-sided t-tests or nonparametric Wilcoxon rank sum test Mann-Whitney two sample statistic. Significance will be set at $p = 0.05$. Secondary endpoint proportions will be assessed using either nonparametric chi-square tests or Fisher's exact test.

Other data such as ICU and hospital lengths of stay and adverse events will be collected, summarized, and described. Exploratory analyses these data may be attempted, but these will be hypothesis generating, given the small sample size used in this pilot study.

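### The Section 11 secondary endpoint reads as one percentage per patient, but it is tested with chi-square or Fisher's exact test without a patient-level threshold or a unit of analysis

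*Combined protocol and SAP*

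**What the plan says.** Section 11 (Study Endpoints) gives one secondary endpoint: "Percentage of time during the 96 hour randomization period that the objective pain score was above mild", where above mild means a score over 4. Section 12 (Pain Assessment) has pain scored "every four hours while the patient is awake using a numeric rating scale (NRS) of 0 to 10", so each patient supplies a series of readings.

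Section 14 (Statistical Analysis) says three relevant things:

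- The secondary endpoint is presented as proportions with "interquartile ranges (secondary endpoint" being the term to which that summary is attached.
- The t-test and the Wilcoxon rank-sum test are assigned to the primary endpoint only.
- For the secondary endpoint: "Secondary endpoint proportions will be assessed using either nonparametric chi-square tests or Fisher's exact test".

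Section 4 (Objectives) lists other secondary endpoints: "total daily opioid requirements for days 1-4, duration of effect and objective pain scores using the numeric rating scale (NRS"). No separate test is named for these.

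**The concern.** Chi-square and Fisher's exact test compare counts of independent units, each of which is a yes or a no. A percentage of time is not such a count. To run the named tests, someone must decide what is counted: individual readings, or patients who pass some threshold. The plan makes neither decision, and a decision left open can be taken after the data are seen.

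The sentence does not suit the Section 4 endpoints either. Daily opioid totals, duration of effect and pain scores are not yes/no. Nor is it needed for adverse events, since the plan says "Other data such as ICU and hospital lengths of stay and adverse events will be collected, summarized, and described" and names no test for them.

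At stake is the only secondary comparison that Section 11 defines. Section 4 says the trial is meant to inform larger multicenter studies, so the result is likely to be reused.

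**Working it through.** The plan gives no power, expected difference or correlation for this endpoint, so there is no planned figure to reproduce.

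**Inputs from the documents.** 17 patients per arm (Section 7); a 96 h period and the NRS >4 criterion (Section 11); scoring every 4 h while awake (Section 12); significance level 0.05 (Section 14).

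**Assumptions.** Scheduled readings per patient number at most 96/4 = 24. With 16 waking hours a day there would be 4 × 16/4 = 16. A range of 12-24 is used. The ICC and the expected percentages are assumed throughout.

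**Step 1: does the test match the endpoint?** An interquartile range needs a spread of values, which points to one percentage per patient. A 2×2 table cannot be filled from 17 percentages per arm without a further rule. NRS >4 is such a rule for a reading, not for a patient's percentage.

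**Step 2: if readings were pooled by arm.** The table would hold 17 × 12 = 204 to 17 × 24 = 408 readings per arm. With m readings per patient, the design effect is 1 + (m − 1) × ICC, and the actual error of a nominal 5% test is about 2 × [1 − Φ(1.96/√(design effect))].

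| ICC | m | Design effect | Type I error |
|---|---|---|---|
| 0.02 | 12 | 1.22 | 7.6% |
| 0.02 | 24 | 1.46 | 10.5% |
| 0.1 | 12 | 2.1 | 17.6% |
| 0.1 | 16 | 2.5 | 21.5% |
| 0.1 | 24 | 3.3 | 28.1% |

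Beta-binomial simulation (17 per arm, 20,000 runs per setting) agrees: about 7-11% at ICC 0.02 and 18-29% at ICC 0.1. Wilcoxon on one percentage per patient stayed at 4.4-5.0% with 16 or 24 readings and ICC from 0 to 0.5.

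**Step 3: if patients were cut to yes/no.** Simulated power, assuming mean percentages of 50% v 30%, ICC 0.2 and 24 readings. Wilcoxon on the uncut percentages gives about 65%.

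| A patient counts as yes if the share of readings >4 is | Fisher | Chi-square (uncorrected) |
|---|---|---|
| above 25% | 35% | 49% |
| above 50% | 31% | 45% |
| above 75% | 7% | 17% |
| above 0 (any score >4) | 0.4% | 2% |

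The Fisher figures at the 25% and 50% cuts move by a few points between runs and with the treatment of values exactly at the cut. The pattern does not.

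**Step 4: from readings to time.** Take 16 readings, 6 of them above 4. As a share of readings this is 6/16 = 37.5%. As a share of 96 h, with unscored hours counted as not above 4, it is 6 × 4/96 = 25%. The plan does not say which is meant.

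**The case against.** *The plan does have a cut-point, NRS >4.* True, and it would be wrong to say that none exists. It applies to a single reading, though, and using readings as the counted unit breaks independence, as Step 2 shows.

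*The interquartile range argues against pooling, so the inflated error may never arise.* This stands. A reader might infer that the plan will pool readings and so carries a false-positive rate of 18-29%. The documents do not support that: they commit to no form of the analysis, and the summary statistic points the other way. The sentence may simply name the wrong test.

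*The power figures depend on the cuts chosen.* This also stands. The loss against Wilcoxon reaches about 65 points for any score >4, and can be well under 10 points with other cuts and a higher ICC. A reader might take the table as a range for the trial; it is not one.

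*This is a pilot of 34 patients.* The hypothesis-generating caveat in Section 14 is attached to other data such as lengths of stay and adverse events. The secondary endpoint has its own named test, following a stated significance level. The small scale limits the consequences but does not make the test fit.

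**Conclusion.** The concern holds. On the most natural reading, the endpoint is one percentage per patient, and the named tests cannot be applied to it without a threshold or unit that the plan does not define. That conclusion needs none of the simulated figures.

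The size of the harm is conditional. Pooling would give too many false positives. A patient-level cut is valid if set in advance, but it is a different endpoint, with power that depends heavily on the cut. The documents give no ICC, number of readings or effect size.

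A reader might infer that the trial's main result is in doubt. It is not: the primary endpoint has its own tests and is untouched. This should be fixed, at the level of one secondary endpoint.

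**What to change.** Replace the quoted sentence in Section 14 with text such as:

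> For each patient we compute the percentage of observed time in the 96 h period with NRS >4, using the scheduled four-hourly scores (or, if chosen in advance, time-weighting all scores). Unscored sleep hours are not imputed. Patients who leave before 96 h contribute their observed time, and their number is reported by arm. Arms are compared with the two-sided Wilcoxon rank-sum test, with median and interquartile range by arm. Continuous Section 4 secondary endpoints (daily opioid totals, duration of effect, NRS scores) are compared by the same test on one value per patient. Chi-square or Fisher's exact test is used only for outcomes that are yes/no per patient.

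Pick one of the two time rules, align the Section 11 wording with it, and fix both before unblinding. An equally weighted share of every recorded score should be avoided: if extra scores were taken at painful moments (an assumption), 6/16 = 37.5% could become 10/20 = 50% with little change in time. If a yes/no endpoint is preferred, state the patient-level cut in advance and accept the possible loss of power.

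The cost is one paragraph. No new data are needed, since "All objective pain and agitation scores reported by the NRS will be collected", and Wilcoxon is already named for the primary endpoint. Two limits remain and should be reported with the result. Scores taken only while awake approximate time. And because "participation is the length of their hospital stay", results for patients who leave early cover only their time in the study.

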15) Provisions to Monitor the Data to Ensure the Safety of Subjects

This study involves minimal risk to the patient, however, the DoD requires an independent research monitor for all clinical studies and thus a medical monitor will be assigned. [name], MD, Professor of Surgery and Vice Chair of Surgery will act as the Data Safety Monitor for this study. Any unanticipated adverse event meeting grade 3 or grade 4 as listed below per the FDA's guidance for industry, will be reported to the study medical monitor. The medical monitor will keep a database of the reported events and will report any of the above adverse events to the FDA's MedWatch. In addition, subjects having experience an adverse

event of Grade 3 or 4 will be followed by the PI for the duration of their hospitalization.

The greatest risk for systemic toxicity is at the time of administration and most often as a result of inadvertent intravenous injection of the drug with rapid onset of symptoms. The procedure will be performed per UCDMC's "Hip Fracture Protocol" which includes routine fascia iliaca compartment blocks, a provider training protocol and routine ultrasound guidance. The protocol also includes telemetry monitoring, continuous pulse oximetry and q 15 min neurologic assessments for 30 min following injection. In addition, the patients will remain on telemetry for an additional 4 hours monitoring for any delayed events.

Following this 4 hour period, evaluation and capture of adverse events will continue until the completion of the 96 hour study period. This will consist of nursing evaluation and vitals every 4 hours around the clock and on an as needed basis. The study coordinator will evaluate for any potential events on a daily basis throughout the study period. The PI or co-PI will be notified directly of any severe adverse event at the time of the event.

The definitions of an adverse event are in line with the WHO-UMC system for standardized case causality assessment.

Causality term	Assessment criteria*
Certain	
• Event or laboratory test abnormality, with plausible time relationship to drug intake• Cannot be explained by disease or other drugs• Response to withdrawal plausible (pharmacologically, pathologically)• Event definitive pharmacologically or phenomenologically (i.e. an objective and specific medical disorder or a recognised pharmacological phenomenon)• Rechallenge satisfactory, if necessary

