- (1) If a subject experiences an adverse event (AE) that renders them incapable of continuing with the remaining study assessments, the subject is to be discontinued. A final evaluation will be performed so that the subject's study participation can be terminated in a safe and orderly manner.
- (2) Patients will be free to discontinue the study at any time, without prejudice to future treatment. These subjects will be encouraged to complete at least the remaining safety assessments.
- (3) Patients will be removed from the study if they refuse either the study drug administration or fail to comply with study procedures.
- (4) In the event that a subject chooses to withdraw from research after data collection has been performed, no additional data will be collected after time of withdrawal.
- (5) There are no foreseeable circumstances necessitating the withdrawal of subjects from research without their consent.

b) Unblinding Criteria

- (1) The blinding of therapy administered will be removed during the study period if evidence of local anesthetic toxicity is present based on the following:
 - (a) Central nervous system reactions manifested by one of the following: paresthesia, acute anxiety, tinnitus or seizure.
 - (b) Cardiac reactions manifested by one of the following: life threatening arrhythmia (ventricular arrhythmia, new onset heart block, new onset QT prolongation, hypotension unresponsive to fluid resuscitation or requiring vasopressor support or CPR).
 - (c) Systemic Allergic reactions manifested by anaphylaxis.

17) Risks to Subjects

Pharmacologic risk:

Administrations of local anesthetics is common place in medical practice, however, there are adverse reactions. Those more frequent are listed below per each specific anesthetic.

Liposomal bupivacaine:

Very Common Adverse Reactions ($\geq 10\%$): nausea, constipation, and vomiting.

Common Adverse Reactions ($\geq 2\%$ to $< 10\%$): pyrexia, dizziness, edema, peripheral, anemia, hypotension, pruritus, tachycardia, headache, insomnia, anemia postoperative, muscle spasms, hemorrhagic anemia, back pain, somnolence, and procedural pain.

Ropivacaine:

Incidence of $\geq 5\%$ in all clinical studies (N=3988): hypotension (37%), nausea (24.8%), vomiting (11.6%), bradycardia (9.3%), fever (9.2%), pain (8%), postoperative complications (7.1%), anemia (6.1%), paresthesia (5.6%), headache (5.1%), pruritus (5.1%), and back pain (5%).

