Incidence 1 to 5%: Urinary retention, dizziness, rigors, hypertension, tachycardia, anxiety, oliguria, hypoesthesia, chest pain, hypokalemia, dyspnea, cramps, and urinary tract infection.

There is also the potential risks of severe life-threatening adverse effects associated with the administration of local anesthetics which are due primarily to toxic systemic concentrations. Risks are associated with toxic plasma concentrations and can be characterized as central nervous system, cardiovascular and allergic reactions and local tissue toxicity. Despite the sustained release and potential for systemic toxicity, in studies to date, the safety profile of Exparel does not appear to differ in a clinically significant way from standard bupivacaine HCl. For the doses studied as part of the FDA clinical development program, there is no evidence that Exparel produces tissue toxicity in the short or long term, that it adversely affects wound healing, or that it is any more likely than bupivacaine HCl to cause neurological or cardiac toxicity with systemic absorption or inadvertent injection.

The greatest risk for systemic toxicity is at the time of administration and most often as a result of inadvertent intravenous injection of the drug with rapid onset of symptoms. As a result, FICBs will be administered in the emergency room where trained personnel and equipment are available to promptly treat patients who show evidence of neurological or cardiac toxicity. The procedure will be performed per UCDMC's "Hip Fracture Protocol" and will include telemetry monitoring, continuous pulse oximetry and q 15 min neurologic assessments for 30 min following injection. In addition, the patients will remain on telemetry for an additional 4 hours for monitor for any delayed events. The FICB is performed laterally, distant from the neurovascular bundle, and under ultrasound guidance minimizing the risk of intravenous injection. The lipid emulsion of the liposomal bupivacaine results in a white milky appearance similar to that of propofol. Steps taken to minimize inadvertent medication error include a recent manufacture change in propofol labeling and storage, handling and delivering of the study drug by the IDS at UCDMC. Patients that exhibit any of the signs or symptoms listed in 16b, will be removed from blinding and 20% lipid emulsion will be administered.

Privacy Risk

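### The rule for reporting to the independent medical monitor covers unanticipated Grade 3–4 events, so foreseen anesthetic toxicity, most clearly an isolated seizure, need not reach the monitor

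*Combined protocol and SAP*

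**What the plan says.** Section 15 explains why there is a monitor: "the DoD requires an independent research monitor for all clinical studies". It then sets the reporting trigger: "Any unanticipated adverse event meeting grade 3 or grade 4 as listed below" goes to the study medical monitor. The monitor keeps a database of what is reported and "will report any of the above adverse events to the FDA's MedWatch". A separate line deals with urgent notice: "The PI or co-PI will be notified directly of any severe adverse event at the time of the event".

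Section 16b(1) lists the signs of local anesthetic toxicity that lead to unblinding. They include "Central nervous system reactions manifested by one of the following: paresthesia, acute anxiety, tinnitus or seizure", a set of cardiac reactions (among them ventricular arrhythmia, new heart block and refractory hypotension), and "Systemic Allergic reactions manifested by anaphylaxis".

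Section 17 states: "There is also the potential risks of severe life-threatening adverse effects associated with the administration of local anesthetics". It adds that the risks "can be characterized as central nervous system, cardiovascular and allergic reactions and local tissue toxicity". For patients with any Section 16b sign, it prescribes unblinding and lipid emulsion.

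The stopping rule is at the end of Section 12. It halts the study for two or more patients on active drug with the same Grade 3 reaction, or for one patient with a reaction of Grade 4 or above.

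**The concern.** The trigger has two conditions. The event must be unanticipated, and it must reach Grade 3 or 4 in the table. The first works against the purpose of the rule: the toxicities that the protocol names in advance, and for which it prescribes rescue, are the hardest to call unanticipated. Followed as written, the rule does not require that the independent monitor hear of a seizure after the block.

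At stake is independent review of the main pharmacologic hazard of the procedure, in a trial whose funder requires an independent monitor. The MedWatch route is also affected, because it runs through the monitor and covers the same set of events.

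**Working it through.** The protocol states no figure on this point, so the check is mainly a reading of the text, with one small calculation of workload.

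**Step 1: does the word narrow the rule?** Section 15 uses the same grades again when it has the PI follow patients with a Grade 3 or 4 event during their hospital stay. That sentence does not contain *unanticipated*. The reporting sentence is therefore narrower than the follow-up sentence.

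**Step 2: are the events in the table?** The severity table has 8 vital-sign rows and 8 systemic rows, 8 + 8 = 16. None is for seizure or anaphylaxis. Seizures are named in one cell, Grade 3 methemoglobinemia (level of 30% or greater).

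**Step 3: apply both conditions.**

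| Event foreseen in Section 16b(1) | Unanticipated, in the ordinary sense? | Grade 3–4 available in the table? |
|---|---|---|
| Isolated seizure | No | No row of its own |
| Ventricular arrhythmia, CPR | No | Yes, Dysrhythmia row |
| Anaphylaxis | No | Only through its signs: systolic pressure below 80 (Grade 3), hypotensive shock (4), respiratory rate above 25 (3), intubation (4) |

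Failing the first condition is enough to remove the duty to report. A seizure graded 4 by judgement would satisfy the second condition but could still be excluded as anticipated.

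**Step 4: is there another route to the monitor?**
- Severe events go to the PI or co-PI (Section 15).
- Section 16b events lead to unblinding and lipid emulsion (Sections 16b and 17).
- The stopping rule names no recipient (Section 12).
- MedWatch reports take their scope from the monitor sentence (Section 15).

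None of these sends a Section 16b event to the monitor. Part of the text between Section 24 and the consent section was not available, so a route there cannot be ruled out.

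**Step 5: workload if every Section 16b(1) event is reported.** Inputs: 17 patients per arm (Section 7); ropivacaine rates of 5.6% for paresthesia and 1 to 5% for anxiety (Section 17). Expected reports = patients × rate.
- Paresthesia: 17 × 0.056 = 0.95
- Anxiety: 17 × 0.01 = 0.17 to 17 × 0.05 = 0.85
- Sum in the ropivacaine arm: 0.95 + 0.17 = 1.12 to 0.95 + 0.85 = 1.80

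Neither sign is in the protocol's list for liposomal bupivacaine. If the ropivacaine rates are simply assumed for all 34 patients, the range doubles to about 2.2 to 3.6. This is an order of magnitude, not a bound. Not every paresthesia or anxiety would be judged evidence of toxicity, and the other Section 16b signs are not counted. The protocol gives no rate for seizure or anaphylaxis, and none is assumed here.

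**The case against.** The strongest reply is that the point turns on an undefined word. Seizure is in neither drug's list of common reactions in Section 17, and patients with a seizure history are excluded. A monitor could fairly call a seizure in such a patient unanticipated. Section 15 also sets a duty to report certain events and does not forbid reporting others. This stands as a limit on certainty. It does not remove the gap, because a safety duty should not depend on how each reader takes the word.

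The missing table row is weaker evidence than it looks. Section 15 says that every potential reaction will be graded under the adapted guidance, so unlisted events can presumably be graded from the column headings. This objection largely stands: the absent row makes the seizure case clearer but does not carry the point.

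A reader might also infer more than the documents support:
- *That a seizure would go unnoticed or untreated.* The block is injected in small increments with aspiration. It is followed by neurologic checks, telemetry and daily coordinator review, and lipid rescue is prescribed.
- *That the trial would carry on regardless.* The stopping rule has no *unanticipated* condition, and the Grade 4 heading refers to life-threatening events, so a seizure would probably stop the study.
- *That an investigator alone sets the grade that decides stopping.* The available text names neither who grades nor who stops.

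**Conclusion.** The point holds in a narrow form. As worded, Section 15 does not clearly require that toxicity foreseen in Sections 16b(1) and 17 be reported to the independent monitor or, through the monitor, to MedWatch. An isolated seizure is the clearest case. Arrhythmia and the signs of anaphylaxis can be graded but may still be excluded as anticipated. Prevention, detection, treatment and notice to the PI are in place, and the stopping rule probably applies as well.

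This rests on two assumptions: that *unanticipated* carries its ordinary meaning, and that the unavailable text holds no further reporting route. Severity is minor and confidence moderate.

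**What to change.** Keep the Section 15 sentence and add a clause: *and any event that triggers unblinding under Section 16b(1), whether or not anticipated and whatever its table grade, will be reported promptly to the medical monitor*. For clarity, add two entries to the severity table placing seizure and anaphylaxis at Grade 4, so that the stopping rule applies to them explicitly.

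Two changes should be avoided. Striking *unanticipated* altogether would send routine Grade 3 events to the monitor and on to MedWatch, such as a systolic pressure above 155 or constipation needing a suppository. The existing hypotension grades already work and should stay as they are.

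The cost is a short amendment with no new staff or procedures. The monitor would receive a few more reports, on the scale worked out above. Because the MedWatch sentence follows on, these would be covered by it too unless the amendment says otherwise. A seizure or anaphylaxis with another cause could pause the 34-patient trial until causality is judged. The exclusions for seizure history and local anesthetic allergy make that less likely.
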